### **Pregnancy**

Patients will be instructed that known or suspected pregnancy occurring during the study, in patients or female partners of male patients, should be confirmed and reported to the Investigator. Any patient who becomes pregnant during the study must be promptly withdrawn from the study. Upon discontinuation from the study, only those procedures that would not expose the patient to undue risk will be performed. The Investigator should also be notified of pregnancy occurring during the study but confirmed after completion of the study. In the event that a patient is subsequently found to be pregnant after inclusion in the study, any pregnancy will be followed to term, and the status of mother and child will be reported to the Sponsor after delivery.

Full details will be recorded in the CRF, or an SAE report will be completed if the patient has completed the study.

## **7.4 Investigational Products Administered**

### **7.4.1 MS1819-SD Administration**

At the time of prescribing, the Investigator or delegated site staff will fill in a source document with the appropriate dosing instructions.

MS1819-SD doses will typically be fractionated as follows: 1/4 of the daily dosage at each 3 main meals, and 1/8 at each of the 2 snacks (eg, for 2240 mg/day will be fractionated as follows: 4 capsules of 140 mg with the morning, noontime, and evening meals; plus 2 capsules of 140 mg with the morning and evening snacks).

Please refer to [Table 2](#) for dosing guidance.

**Table 2: MS1819-SD Typical Dosing Schedule**

	Dose: 2240 mg/day
Breakfast	4 x 140 mg capsules
Snack 1	2 x 140 mg capsules
Lunch	4 x 140 mg capsules
Snack 2	2 x 140 mg capsules
Dinner	4 x 140 mg capsules
Total	16 (140 mg) capsules/day

Note: Individual variations may occur as long as correct total daily dose is achieved.

#### **7.4.2 Porcine PERT**

Patients will take their porcine PERT at the same dose that was being administered during the prestudy period, during the appropriate treatment period.

#### **7.4.3 Method of Assigning Patients to Treatment Groups**

Patients will be randomized 1:1.

#### **7.5 Previous and Concomitant Therapy**

Standard-of-care medications are allowed (eg, antibiotics, mucolytic agents, aerosols, CFTR modulators). Patients taking CFTR modulators should be on stable doses for at least 3 months. Patients should not start taking CFTR modulators during the duration of the study.

Gastric acid suppressants are allowed but must be on stable dosage for 30 days before screening and must not be altered in dose or stopped during the study.

Prohibited medications during the entire clinical study will be as follows:

- Orlistat lipase inhibitor (eg, Alli®, Xenical®)
- Laxatives consisting of mineral oil and castor oil; chronic use of osmotic laxatives is permitted

- Symptomatic treatments of diarrhea: loperamide (eg, loperamide generic, Imodium®, Imodium A-D®, Diamode®, Imotil®, Kao-Paverin®); atropine/diphenoxylate (Lonox®); and atropine/diphenoxylate (Lomocot®).

## 7.6 Study Drug Materials and Management

### 7.6.1 MS1819-SD

Study drug MS1819 will be supplied by the Sponsor for use in the protocol and is limited to investigational use only. Please refer to current Investigator's Brochure for additional information.

MS1819-SD is 70% pure preparation of LIP2 protein. The concentrated ultra-filtration product obtained from fermentation is mixed with maltodextrin (1:2 ratio, based on the lipase dry weight) and subjected to spray drying (i.e., the drug substance). The drug product is formulated with inactive excipients and formulated in nonanimal origin capsules of hydroxypropylmethyl cellulose (also named HPMC or hypromellose). MS1819-SD capsules will be used in the study with 140 mg active pharmaceutical ingredient in each capsule.

MS1819-SD will be supplied as per following dosage form and will be provided in blister packs (wallets) in boxes:

- A white hard HPMC capsule filled with an off-white to light grey powder containing approximately 140 mg of MS1819-SD.

#### 7.6.1.1 MS1819-SD Shipment, Receipt, and Storage

MS1819-SD will be supplied in blister packs to the sites by the Sponsor, in accordance with local requirements. The IMP will be shipped at room temperature. The site is responsible for the appropriate storage of the IMP. The IMP must be stored in a secured limited-access area and maintained at room temperature  $\leq 25^{\circ}\text{C}$ .

#### 7.6.1.2 MS1819-SD Misuse/Overdose

Any IMP misuse or overdose associated or not associated with any AE should be reported to the Sponsor or designee as an SAE. Overdose is considered as dose taken above the prescribed daily dose for the current dosing phase.

### 7.6.1.3 MS1819-SD and porcine PERT Compliance

The Investigator is responsible for ensuring compliance. Compliance with MS1819-SD and porcine PERT will be cross-checked with IMP accountability (number of capsules and blisters)

### 7.6.1.4 MS1819-SD Supply, Resupply, and Accountability

On receipt, the pharmacist or delegated site staff will record the date, details of the bottle, and quantity of capsules.

The investigational sites will be re-supplied with IMPs according to their respective recruitment rates.

The pharmacist or delegated site staff will be provided with specific forms for accountability of the IMP (including the returned blisters). Records will be kept up-to-date throughout the study and must be complete and accurate.

Used and unused IMPs must be made available to the Monitor or Sponsor designee who will verify the IMP accountability and cross-check pharmacy and Investigator records for compliance to the protocol requirements. Any discrepancy must be accounted for and documented.

### 7.6.1.5 MS1819-SD Return, Destruction, and Recall

Return of IMP:

- Unused, partially used, or empty blisters will be returned by the patient to the site at the end of each cycle.
- At the end of the study, the Sponsor will conduct a final reconciliation between delivered, dispensed, and used/unused IMPs.

Destruction of IMP:

- Unused, partially used, or empty blisters must not be destroyed at the Investigative Sites without written authorization from the Sponsor.
- Unused, partially used, or empty blisters returned to the pharmacy will be destroyed at the Hospital Pharmacy or Sponsor's Drug Distributor only after IMP accountability forms have been fully and accurately completed and verified by the Monitor.

---

- If an on-site destruction is required, then the site must obtain written authorization for destruction from the Sponsor, which will be filed along with the certificate of destruction in the IMP section of the pharmacy site file.

Recall:

- If an IMP batch is suspected to be defective, then the Sponsor will immediately inform the Investigator and the hospital pharmacist.
- The Monitor will coordinate with the investigative site staff for the return of the concerned batches as per the return procedure. Depending on the study status, new batches may be sent to the investigational site.

## **7.6.2 Nonabsorbable Dye Marker**

The dye marker FD&C Blue #2, also named Indigo carmine or Indigotin, will be supplied in accordance with current Good Manufacturing Practices (cGMP).

### **7.6.2.1 Shipment, Receipt, and Storage and Dispensing**

The dye marker will be supplied. The dye makers should remain between 15–25°C (room temperature) and will not require temperature monitoring during shipment and storage. The bottle must be placed in secure location at site.

## 8. TIMING OF STUDY PROCEDURES

Patients will provide written informed consent before any study-related procedures are performed.

The study Schedule of Assessments is included in [Section 7.1.1 \(Table 1\)](#).

### 8.1 Screening Period

Throughout the screening period, Patients are to remain on their prestudy porcine PERT.

#### 8.1.1 Visit 1, D-21 to D1: Screening Visit

The following procedures will be performed at the Screening Visit (which may take place over more than one day):

- Obtain signed informed consent from the patient before any study-related assessments are made
- Collect relevant medical history, including concomitant illnesses/diseases, previous/concomitant medications, and record AEs
- Complete physical
- Specific CF assessment including a pulmonary function test by spirometry to determine FEV1 >30% of predicted normal for age, sex, and height at screening and a sweat chloride test
- Record body height and weight
- Record vital signs while sitting (blood pressure, pulse rate, breathing rate, and temperature)
- Assess for eligibility (against the inclusion and exclusion criteria)
- Record demographic data such as ethnic origin, date of birth, and sex
- Collect urine sample for urinalysis
- Perform a serum pregnancy test, if applicable
- Collect samples for hematology, clinical chemistry, PT/INR, activated partial thromboplastin time (aPTT)
- Collect blood samples for vitamin determination (A, D, E, and K)

- Patients will be required to fast before the collection of screening laboratory tests.
- Collect samples for fasting lipids and prealbumin
- Obtain a stool sample for fecal pancreatic elastase concentration in the selected central laboratory

### **8.1.2 Visit 2 Telephone (T)**

Once patient eligibility is confirmed, patients will be contacted by telephone and instructed to:

- Refrain from alcohol consumption for 24 hours before the visit
- Bring their prestudy porcine PERT with them to the clinic in the event they are randomized to their prestudy PERT

## **8.2 First Treatment Period (Visits 3, 4 (T), 5 (T), and 6)**

### **8.2.1 Visit 3 (Day 1): Randomization Visit - Must Occur Within 21 Days of Visit 1**

During the first treatment period, patients will be randomized to either a fixed dose of MS1819-SD or to their prestudy porcine PERT. Visit 3 will take place if the patient is eligible to continue on the basis of data obtained at the Screening visit. The following procedures will be performed:

- Review Inclusion /Exclusion Criteria
- Focused physical exam to evaluate gastrointestinal tract, heart, and lungs
- Record body height and weight
- Record vital signs while sitting (blood pressure, pulse rate, breathing rate, and temperature)
- Record any changes in AEs and concomitant medication
- Randomization to either a fixed dose of MS1819-SD or to continue their prestudy porcine PERT
- Instruct patients on use and dosing
- Instruct/dispense study drug to patient (if randomized to MS1819-SD), otherwise patients are to continue on their prestudy porcine PERT

- Assess and record malabsorption signs and symptoms
- Collect urine sample for urinalysis
- Perform a urine pregnancy test (urine dip stick), if applicable
- Collect blood samples for vitamin determination (A, D, E, and K)
- Collect a serum sample for circulating anti-LIP2 lipase antibodies and MS1819-SD concentrations

### **8.2.2 V4 (T) (Day 8 ± 2) and V5 (T) (Day 15 ± 2)**

The following procedures will be performed:

- Record any changes in AEs and concomitant medication review.
- Assess and record malabsorption signs and symptoms
- Confirm patient scheduled date for V6 (first stool collection in supervised controlled setting) and remind patients to come in fasted status.

### **8.2.3 Visit 6: Stool Collection in Controlled Supervised Facility (Day 17 ± 7)**

Patients will be admitted for a maximum of 7 days to a facility providing supervised confinement for collection of stool for determination of CFA, CNA, and stool weight. The timing of the previous visits (Visit 1 and Visit 2) should be made with the aim of accommodating the patients' schedules for the supervised confinement. To accommodate patients' schedules for the supervised confinement, a ±7 day visit window is permitted.

- During the third week (Visit 3) (±1 week), patients will undergo admission to a controlled supervised facility for stool collection to support the CFA and CNA assessment and weight. A ±7 day visit window is allowed to accommodate investigative site staff and patients schedules for the supervised confinement.
- After appearance of fecal stool dye markers has been measured, patients CFA and CNA will be measured under their dose of MS1819-SD or prestudy dose of porcine PERT using standardized high-fat meals during the 3-day standardized diet.
- The CFA calculation will be based on the measured fecal fat content in relation to ingested fat quantities during the 3-day stool collection period.

After completion of the initial treatment period during the completion of V3, patients will be instructed to switch their study medication to either a fixed dose of MS1819-SD or their

---

prestudy porcine PERT. The stool collection and dietary procedures will be conducted as described in Section 8.3.3.1. (Instructions for Supervised Confinement)

The following procedures will be performed at Visit 6:

- Focused physical exam to evaluate gastrointestinal tract, heart, and lungs
- Record body height and weight
- Record vital signs while sitting (blood pressure, pulse rate, breathing rate, and temperature)
- Record any changes in AEs and concomitant medication
- Instruct/dispense study drug
- Verify study drug count on the last day of confinement
- Return MS1819-SD (only for patients randomized to MS-1819SD) on the last day of confinement
- Assess and record malabsorption signs and symptoms
- Begin 72-hour controlled diet
- Marker-to-marker stool collection and stool weight (central laboratory will weigh the stool that is collected)
- Collect urine sample for urinalysis
- Perform a urine pregnancy test (urine dip stick), if applicable
- Collect samples for hematology, clinical chemistry, PT/INR, and aPTT
- Collect samples for fasting lipids and prealbumin
- Collect blood samples for vitamin determination (A, D, E, and K)
- Collect a serum sample for circulating anti-LIP2 lipase antibodies and MS1819-SD concentrations
- Record all fat, protein, and dose of study drug taken with every meal and snack during the confinement period

At the end of the supervised confinement (once the second blue dye marker sample has been collected), patients will crossover to their new treatment). Patients randomized to MS1819-SD will begin treatment on their prestudy porcine PERT. Patients randomized to their prestudy porcine PERT will begin treatment on MS1819-SD.

## 8.3 Second Treatment Period (Visits 7 [T], 8 [T] and 9)

The second treatment period will begin once patients have passed their second blue dye marker at the end of V6, and the stool sample collection is complete. As soon as this has occurred, patients will crossover to their new treatment (either MS1819-SD or patient's prestudy porcine PERT).

### 8.3.1 V7 (T) (Day 29 ± 2) and V8 (T) (Day 36 ± 2)

The following procedures will be performed:

- Record any changes in AEs and concomitant medication review.
- Assess and record malabsorption signs and symptoms
- Confirm patient scheduled date for V9 (second stool collection in supervised controlled setting) and remind patients to come in fasted status.

### 8.3.2 Visit 9: Stool Collection in Controlled Supervised Facility (Day 38 ± 7)

Patients will be admitted for a maximum of 7 days to a facility providing supervised confinement for collection of stools for determination of CFA, CNA and stool weight. The stool collection and dietary procedures will be conducted as described in Section 8.3.3.1 (Instructions for Supervised Confinement). The following procedures will be performed at Visit 9:

- Focused physical exam to evaluate gastrointestinal tract, heart, and lungs
- Record body height and weight
- Record vital signs while sitting (blood pressure, pulse rate, breathing rate, and temperature)
- Record any changes in AEs and concomitant medication
- Instruct/dispense study drug
- Verify study drug count on the last day of confinement
- Return MS1819-SD (only for patients that crossed over to MS-1819SD) on the last day of confinement
- Assess and record malabsorption signs and symptoms
- Begin 72-hour controlled diet

- Marker-to-marker stool collection and stool weight (central laboratory will weigh the stool that is collected)
- Collect urine sample for urinalysis
- Perform a urine pregnancy test (urine dip stick), if applicable
- Collect samples for hematology, clinical chemistry, PT/INR, and aPTT
- Collect samples for fasting lipids and prealbumin
- Collect blood samples for vitamin determination (A, D, E, and K)
- Collect a serum sample for circulating anti-LIP2 lipase antibodies and MS1819-SD concentrations
- At the end of the supervised confinement (once the second blue dye marker sample has been collected):
  - All patients are to resume therapy on their prestudy porcine PERT. Patients who crossed over to MS1819-SD will resume treatment on their prestudy porcine PERT; Patients who crossed over to their prestudy PERT will continue with their prescribed therapy.
  - Patients on MS1819-SD will return all study drug.
- Remind patients of their scheduled Visit 10 date

### 8.3.3 Visit 10: End-of-Study /Early Withdrawal Visit (Day 56 ± 2)

Patients will return to the clinic for their End of Study visit approximately 2 weeks after their last dose of study drug (either MS1819-SD or the patient's prestudy porcine PERT). In the event that patients do not complete V9, an Early Withdrawal visit will be held approximately 2 weeks after the last dose of study drug (either MS1819-SD or the patient's prestudy porcine PERT). The procedures scheduled for the End-of-Study visit are the same as those that should be conducted for the Early Withdrawal visit. The following procedures will be performed at the End-of-Study/Early Withdrawal Visit:

- Focused physical exam to evaluate gastrointestinal tract, heart, and lungs
- Record any changes in AEs and concomitant medication
- Assess and record malabsorption signs and symptoms
- Collect a serum sample for circulating anti-LIP2 lipase antibodies and MS1819-SD concentrations
- Collect blood samples for vitamin determination (A, D, E, and K)

- Perform a urine pregnancy test (urine dip stick), if applicable

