### 7.1.1 Schedule of Assessments

**Table 1: Schedule of Assessments**

	SCREENING		INITIAL TREATMENT PERIOD			SECOND TREATMENT PERIOD			END OF STUDY/EARLY TERMINATION	
	1 a	2 (T) b	3	4 (T) c	5 (T) c	6 d	7 (T) c	8 (T) c		
Visit Number	1 a	2 (T) b	3	4 (T) c	5 (T) c	6 d	7 (T) c	8 (T) c	9 d	10
Study Week	-3		1	1	2	3	4	5	6	8
Study Days	-21		1	8	15	17	29	36	38	56
Visit Window (days)	V1 to V2 interval $\leq$ 21 days			$\pm$ 2	$\pm$ 1	$\pm$ 7	$\pm$ 2	$\pm$ 2	$\pm$ 7	$\pm$ 2
Confirm scheduled date for next supervised confinement visit				X	X		X	X		
Study Treatment										
Randomization			X							
Instruct regarding prestudy PERT/Dispense study drug MS1819-SD			X			X			X	
Verify study drug count at the end of confinement						X			X	
Return MS1819-SD (only for those on MS1819-SD) at the end of confinement						X			X	
Record fat and protein intake and study drug taken at all meals and snacks						X			X	

	SCREENING		INITIAL TREATMENT PERIOD			SECOND TREATMENT PERIOD			END OF STUDY/EARLY TERMINATION	
	1 a	2 (T) b	3	4 (T) c	5 (T) c	6 d	7 (T) c	8 (T) c		
Visit Number	1 a	2 (T) b	3	4 (T) c	5 (T) c	6 d	7 (T) c	8 (T) c	9 d	10
Study Week	-3		1	1	2	3	4	5	6	8
Study Days	-21		1	8	15	17	29	36	38	56
Visit Window (days)	V1 to V2 interval $\leq$ 21 days			$\pm$ 2	$\pm$ 1	$\pm$ 7	$\pm$ 2	$\pm$ 2	$\pm$ 7	$\pm$ 2
Cross over to alternative treatment f						X				
Efficacy Measures										
Malabsorption signs & symptoms			X	X	X	X	X	X	X	
72-hour controlled diet record						X			X	
Marker-to-marker stool collection and stool weight g						X			X	
Laboratory Tests										
Urinalysis	X		X			X			X	
Pregnancy test (serum for V1 screening and urine dipstick for other visits) h	X		X			X		X	X	
Hematology, clinical chemistry, PT/INR, and aPTT i	X					X			X	
Fasting lipids (patient to come in)	X					X			X	

	SCREENING		INITIAL TREATMENT PERIOD			SECOND TREATMENT PERIOD			END OF STUDY/EARLY TERMINATION	
	1 a	2 (T) b	3	4 (T) c	5 (T) c	6 d	7 (T) c	8 (T) c		

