#### 7.3.4 Removal of Patients from the Study

A patient may be withdrawn from the study at any time for any of the following reasons:

- Loss to follow-up
- Withdrawal of consent, for any reason, at any time
- Major protocol deviations that could compromise the interpretation of the results
- Occurrence of an immunoallergic reaction
- Occurrence of an adverse reaction (ie, an SAE related to IMP) that justifies the discontinuation of the IMP
- Pregnancy

The date of withdrawal and the reason for withdrawal must be fully documented in the case report form (CRF) and a short narrative description should be added in the patient's medical records.

If at the time of withdrawal, the patient has received the investigational study product (partially or totally), study staff should encourage the patient to attend the Early Withdrawal

---

Visit for follow-up safety investigations. These patients will be included in the ITT efficacy analysis and safety analysis.

If the reason for discontinuation is an AE, then the Investigator will seek to obtain follow-up information and to document the event until its resolution or stabilization. In any case, the Investigator will take all necessary measures to ensure the patient's safety and ensure the patient is treated in accordance with local standard of care.

If a patient is lost to follow-up, then the Investigator should make every effort to obtain maximum information on the reasons for the nonattendance to the visit and on the patient's state of health. All attempts will be documented in the patient's medical records.

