## 9.2 Reporting Procedures for All Adverse Events

AEs will be recorded in the CRF for all patients from the time the patient signs the informed consent form through the end of the study or patient withdrawal.

The Investigator is responsible for ensuring that all AEs (as defined in [Section 9.1](#) and as further specified below) observed by the Investigator or reported by patients are collected and recorded in the patients' medical records, in the CRF, and as an SAE in the electronic data capture system. These AEs will include the following:

1. All SAEs (as defined in [Section 9.1.2](#)) that occur.
2. All nonserious AEs (as defined in [Section 9.1.1](#)) that occur.

The following AE attributes must be assigned by the Investigator:

- AE diagnosis or syndrome(s) (if known, signs or symptoms if not known);
- event description (with detail appropriate to the event);
- dates of onset and resolution; severity; assessment of relatedness to study drug; and
- action taken with study medication.

The Investigator may be asked to provide follow-up information, discharge summaries, and extracts from medical records or CRFs.

It will be left to the Investigator's clinical judgment to determine whether the relatedness of an AE, and of sufficient severity to require the patient's removal from treatment or from the study. A patient may also voluntarily withdraw from treatment because of what he or she perceives as an intolerable AE. If either of these situations arises, the patient should be strongly encouraged to complete the End-of-Therapy assessments and be under medical supervision until symptoms cease or the condition becomes stable.

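### A patient who leaves the study before the MS1819 confinement visit has no scheduled haematology, chemistry, coagulation or urinalysis after MS1819, and Protocol 9.2 contradicts other sections on AE recording after withdrawal

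*Protocol*

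**What the plan says.** Protocol 7.3.4 asks staff to encourage a withdrawn patient who has received study product to attend the Early Withdrawal "Visit for follow-up safety investigations", and it places these patients in the safety analysis. Protocol 8.3.3 sets the timing: "an Early Withdrawal visit will be held approximately 2 weeks after the last dose of study drug". It also sets the content: "The procedures scheduled for the End-of-Study visit are the same as those that should be conducted for the Early Withdrawal visit". The list has a focused physical examination, AEs and concomitant medication ("Record any changes in AEs and concomitant medication"), malabsorption symptoms, one serum sample ("Collect a serum sample for circulating anti-LIP2 lipase antibodies and MS1819-SD concentrations"), vitamins A, D, E and K, and a urine pregnancy test where applicable.

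The row "Hematology, clinical chemistry, PT/INR, and aPTT" of the Schedule of Assessments is marked at Visits 1, 6 and 9 in SAP 13.2. Urinalysis and vital signs are marked at Visits 1, 3, 6 and 9. None of the three is marked at Visit 10.

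The protocol synopsis counts laboratory values among the safety endpoints, and Protocol 7.2.3 names haematology, biochemistry and urinalysis.

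On adverse events, Protocol 9.2 has recording run "through the end of the study or patient withdrawal". For a patient who leaves because of an AE, it adds that "the patient should be strongly encouraged to complete the End-of-Therapy assessments". No visit in the plan has that name, although Protocol 9.5 also refers to an End-of-Therapy CRF.

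**The concern.** The Early Withdrawal visit is the only scheduled contact for a patient who leaves early, and the protocol gives it a safety purpose. Yet it collects none of the routine safety laboratory tests that 7.2.3 names. Reasons for withdrawal in 7.3.4 include an immunoallergic reaction and a drug-related SAE. A patient withdrawn for either before the MS1819 confinement leaves with no scheduled liver, renal, haematology or coagulation result after exposure.

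This matters more here than in most trials. Protocol 10.1 states that the primary goal is to establish the safety of the chosen dose, and Protocol 5.8 says this is the first study of MS1819-SD in CF. SAP 8.5 summarizes haematology, chemistry and the ALT, AST and bilirubin elevations at Screening and 3 weeks after first dose. The MS1819 column of those tables would then describe mainly patients who stayed on the drug until confinement, although SAP 4.3 counts everyone dosed in the safety population.

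The AE texts raise a second issue. A site that reads 9.2 literally could leave out a new non-serious AE arising after withdrawal, although SAP 8.3 has a category for it.

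**Working it through.** **1. Tests by visit.** Read from SAP 13.2 and checked against the procedure lists in Protocol 8.1.1 to 8.3.3.

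| Item | V1 | V3 | V6 | V9 | V10 / Early Withdrawal |
|---|---|---|---|---|---|
| Haematology, chemistry, coagulation | yes | no | yes | yes | no |
| Urinalysis | yes | yes | yes | yes | no |
| Vital signs | yes | yes | yes | yes | no |
| Anti-LIP2 antibodies, MS1819 concentration | no | yes | yes | yes | yes |
| Vitamins A, D, E, K | yes | yes | yes | yes | yes |
| Pregnancy test, if applicable | yes | yes | yes | yes | yes |

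**2. Who is affected.** Crossover happens at the end of Visit 6, so there are four cases of withdrawal from the study:

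- MS1819 first, leaves before Visit 6: the last haematology and chemistry are from screening and the last urinalysis is from Visit 3, the randomization visit. Nothing from these panels follows MS1819. Affected.
- MS1819 first, leaves after Visit 6: the Visit 6 panel was drawn on MS1819. Not affected.
- PERT first, leaves before Visit 6: never took MS1819. Not affected.
- PERT first, leaves between Visits 6 and 9: the Visit 6 panel was drawn on PERT, before crossover. Nothing from these panels follows MS1819. Affected.

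**3. Does hepatic monitoring close the gap?** Protocol 9.7 and footnote I of Table 1 provide unscheduled testing once a new rise in liver tests has been seen. In the two affected cases no scheduled draw after MS1819 could show a rise, so the gap stays open.

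**4. How many.** The plan's own figure first: 30 completers / (1 − 0.20) = 37.5, rounded up to 38, as in Protocol 7.3.1. Planned non-completers: 38 − 30 = 8, and 8/38 = 21%. The documents do not say when dropouts occur or on which treatment, so the number in the two affected cases is anywhere from 0 to 8.

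**5. What the missing patients do to precision (illustration).** With no events among n patients, the one-sided 95% upper limit is 1 − 0.05^(1/n). For n = 30 it is 9.5%; for n = 38 it is 7.6%. The two-sided 95% version, 1 − 0.025^(1/n), gives 11.6% and 9.3%. The move from 30 to 38 is the extreme case, in which all 8 dropouts are affected and all attend the visit. Even then the gain is modest. The stronger argument is which patients are missing, not how many.

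**6. AE recording after withdrawal, side by side.**

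- Protocol 9.2: recording stops at the end of the study or at withdrawal.
- Protocol 8.3.3: AE changes are recorded at a visit about 2 weeks after the last dose.
- Protocol 7.3.4: an AE that caused discontinuation is documented until it resolves or stabilizes.
- Protocol 9.5: SAEs are recorded through the end of study, with no cut-off at withdrawal.
- SAP 8.3: events after the last study period are follow-up TEAEs, expressly including patients who stop before period 2.

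The first text cannot be applied literally together with the others.

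**The case against.** A fair defence has four parts.

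First, the visit is not empty of laboratory work. A reader might infer that such a patient has no post-dose laboratory value at all. That is wrong: antibodies, MS1819 concentration and vitamins are scheduled, and 7.2.3 lists the first two among the safety laboratory results. For an immunoallergic withdrawal the antibody sample is directly relevant. The gap is confined to haematology, chemistry, coagulation and urinalysis, plus vital signs. Vital signs are not a protocol safety endpoint, although SAP 8.6.1 summarizes them.

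Second, a reader might infer from 9.2 that AE capture ends on the day of withdrawal. The sections in step 6 do not support that. The defect is a conflict of wording, and the documents do not show that AE data would be lost.

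Third, stopping capsules is not the same as leaving the study. The documents do not say whether a patient who only stops MS1819 still attends Visit 6 or 9. If so, the panels remain scheduled for that patient.

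Fourth, 20% is a planning allowance. Splitting the 8 dropouts by treatment, for example half on MS1819, has no source. Nor do the documents show that those who leave are those who were harmed: 7.3.4 also lists loss to follow-up, withdrawn consent, protocol deviations and pregnancy.

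All four limit the claim. None of them puts a routine panel into the Early Withdrawal visit.

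**Conclusion.** The point holds in this form. For a patient who withdraws from the study before the confinement visit of the MS1819 period, no haematology, chemistry, coagulation or urinalysis is scheduled after MS1819. That does not match the purpose that 7.3.4 gives the Early Withdrawal visit or the laboratory safety endpoints. The size is 0 to 8 of 38 patients (up to 21%). It rests on the planned 20% dropout and on reading withdrawal as leaving the study, not merely stopping the drug. Protocol 9.2 separately contradicts 8.3.3, 7.3.4 and SAP 8.3 on AE recording after withdrawal, and the passages must be reconciled. This is a gap in data collection that should be closed because it is cheap to close. It does not invalidate the safety analysis.

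**What to change.** - **Visit content.** Add the existing haematology, chemistry and coagulation panel, urinalysis and vital signs to the Early Withdrawal visit in Protocol 8.3.3, Table 1 and SAP 13.2. The blood draw already made there can be used. Because 8.3.3 gives End-of-Study and Early Withdrawal one list, mark the additions as Early Withdrawal only; otherwise completers would have them too.
- **Reporting.** Show these values in SAP 8.5 as a separate follow-up row or listing by last treatment received. Do not pool them with the values at 3 weeks after first dose. They are drawn about 2 weeks after the last dose, and Protocol 9.7 has patients taken off study drug back on porcine PERT, so pooling would mix on- and off-treatment results.
- **AE window.** Reword Protocol 9.2 so that AE recording for withdrawn patients runs through the Early Withdrawal visit, as 8.3.3 and SAP 8.3 already assume. Define the End-of-Therapy terms in 9.2 and 9.5, or replace them with the visit that exists.
- **Clarification.** State whether a patient who only stops MS1819 still attends Visit 6 or 9.

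The cost is a small amendment, with extra tubes and a urine sample at an existing visit for about 8 patients. Patients who do not attend that visit will still have no result.
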